7.2. Protocol Deviations

A summary of subject-specific protocol deviations will be presented by the reason for the deviation, the deviation category, and study arm for all subjects (Table 6). Deviations that are considered major deviations that will be reviewed for possible subject exclusion from the per protocol population include: second or third study vaccination not received, second or third study vaccination received out of window, receipt of non-study licensed live vaccine within 30 days before or 21 days after each study vaccination, receipt of non-study seasonal influenza vaccine (live or inactivated) within 30 days before or for the duration of the study, and receipt of immunosuppressive therapy within 30 days before or after each of the first two study vaccinations. All subject-specific protocol deviations and non-subject specific protocol deviations will be included in Appendix 3 as data listings (Listing 3 and Listing 4, respectively).

8. IMMUNOGENICITY EVALUATION

Analysis of all immune responses will be conducted using the PP population. In addition, for the primary endpoint, analysis conducted with the mITT population will be used as a sensitivity analysis. Percentages of cell subset responses will be measured by flow cytometry as described in Section 4.5.2.

Data listings of HAI and Neut assay results as reported by the central immunogenicity laboratory will be provided in Listing 8, Listing 9, Listing 10, Listing 11, Listing 12, Listing 13, Listing 14, and Listing 15. ELISA assay results will be provided in Listing 16, and flow cytometry results will be provided in Listing 17 and Listing 18.

8.1. Primary Immunogenicity Analysis

The primary immunogenicity objective is to determine whether priming with M-001 improves T cell responses. The cells are sorted via flow cytometry, and the percentages of CD4+ and CD8+ T cells expressing perforin, CD107a, IFN γ , TNF- α , IL-2, or any combination of these are calculated as the number of cells positive for these proteins divided by the total number of T cells counted in each sample. To compare the T cell responses between groups, the following Poisson regression model will be fit for each combination of proteins of interest:

$$log(E(Y|X)/Z)=\beta_0+\beta_1*X,$$

where Y is the number of cells expressing a given combination of proteins, X is an indicator variable for Group A, and Z (the offset) is the total number of T cells in each sample. Wald tests will be performed to evaluate whether there are differences in the expression of T cell subsets between the two study arms. As described in Section 6.8, adjustments for multiple comparisons are not planned.

GMPs of CD4+ and CD8+ T cells expressing each combination of proteins and the corresponding 95% bootstrap confidence intervals will also be presented for each study armTable 22Table 23Table 24Table 25. These will be presented in Table 22, Table 23, Table 24, and Table 25 and summarized visually in boxplots over time in Figure 2, Figure 3, Figure 4, and Figure 5.

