3.3. Study Definitions and Derived Variables

Geometric mean percentages (GMPs) are calculated as the product of the observed percentages raised to the 1/Nth root, where N is the number of observed values.

The baseline value for cellular and humoral immunity will be defined as the value obtained on Day 1 prior to M-001 vaccination.

M-001 antibody response after baseline will be summarized by GMTs and the proportion of subjects achieving seroconversion (defined as a minimum four-fold rise in post-vaccination ELISA antibody titer) at each time point, with corresponding 95% confidence intervals.

For individual subjects, fold rise will be calculated as the ratio of: $\frac{post-vaccination\ titer}{pre-vaccination\ titer}$, where pre-vaccination value is always the result obtained at Day 1, prior to the first M-001 dose.

Seroconversion for HAI and Neut assays is defined as either a pre-vaccination titer < 1:10 and a post-vaccination titer $\ge 1:40$, or a pre-vaccination titer $\ge 1:10$ and a minimum four-fold rise in post-vaccination titer.

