5. SAMPLE SIZE CONSIDERATIONS

The study population for this clinical trial was planned to include 120 males and non-pregnant females, 18 to 49 years old, inclusive, who are in good health and meet all eligibility criteria. The subjects were recruited from the general population at the participating VTEU sites that have substantial experience conducting large influenza vaccine studies.

Based on the accrual rate for similar studies, it was expected that the participating VTEUs would be able to enroll this trial in a timely fashion. Prior experience suggests up to 5% of subjects could be excluded from the per protocol analysis for the primary immunogenicity outcome either because they are lost-to-follow-up or otherwise do not have data available following the second study vaccination or because they had a protocol deviation requiring their exclusion from the per protocol analysis.

Table 3 indicates the probability of observing one or more safety events, such as solicited injection site or systemic reactogenicity events or an unsolicited non-serious AE of a particular type, for a single study arm (N=60) and all enrolled subjects (N=120).

Binomial confidence intervals (CI) are widest (have the least precision) when the response rate is 50%. Table 4 is presented to indicate the worst-case scenario for precision of observed exact (Clopper-Pearson) binomial confidence intervals.

With N=60 subjects per arm and assuming the standard deviation of log GMP is 0.75, the study will have 80% power to detect a 2.5-fold increase in the GMP of T cell subsets expressing IFN-γ. Table 5 illustrates a power analysis considering a range of standard deviations for log GMP and a range of GMP fold-change with N=60 subjects per arm, and further includes the power under the conservative assumption of 10% drop out in each study arm. Power is calculated for a two-sided t-test with significance level (alpha) 0.05 using PROC POWER in SAS 9.4. Utilizing different tests instead of those based on Normal approximations could increase the power from what is shown.

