While there will be multiple comparisons performed for this primary immunogenicity objective (for each of five parameters alone measured in CD4 and CD8 T cells plus any combinations measured), it is assumed that these analyses are not intended to be confirmatory and thus no adjustment for multiple comparisons is considered. Instead, p-value thresholds of p<0.001, p<0.01, and p<0.05 will be considered as strong, moderate, and weak evidence of differences between study arms. These will be indicated in relevant tables with ***, **, and *, respectively.

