12. SUMMARY OF CHANGES IN THE CONDUCT OF THE STUDY OR PLANNED ANALYSES

After the data format for the primary analysis was confirmed, the planned analysis was changed from what is described in the protocol. Instead of utilizing a normal approximation, a Poisson regression model will be fit to test for differences between study arms, as described in Section 8.1.

Additionally, the modified Intent-to-Treat population will only be used as a sensitivity analysis for the primary objective. Originally it was also planned for secondary and exploratory objectives involving antibody responses, but these will not be done in the interest of conciseness.

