[Implementation Note: Do not include p-value column for Tables 28-31, and only include it for Day 36 for Tables 25-27. Include rows for any perforin, any CD107a, any IFN- γ , any TNF- α , and any IL2.]

- Table 23: Geometric Mean Percentage (GMP) of CD8+ T Cell Subsets Expressing Markers Alone or in Combination After M-001 Stimulation with 95% Confidence Intervals by Study Day and Study Arm, Per Protocol Population*
- Table 24: Geometric Mean Percentage (GMP) of CD4+ T Cell Subsets Expressing Markers Alone or in Combination After M-001 Stimulation with 95% Confidence Intervals by Study Day and Study Arm, Modified Intent-to-Treat Population*
- Table 25: Geometric Mean Percentage (GMP) Of CD8+ T Cell Subsets Expressing Markers Alone or in Combination After M-001 Stimulation with 95% Confidence Intervals by Study Day and Study Arm, Modified Intent-to-Treat Population*
- Table 26: Percentage of CD4+ T Cell Subsets Expressing Markers Alone or in Combination After Seasonal Influenza A Antigen Stimulation with 95% Confidence Intervals by Study Day and Study Arm, Per Protocol Population
- Table 27: Percentage of CD8+ T Cell Subsets Expressing Markers Alone or in Combination After Seasonal Influenza A Antigen Stimulation with 95% Confidence Intervals by Study Day and Study Arm, Per Protocol Population
- Table 28: Percentage of CD4+ T Cell Subsets Expressing Markers Alone or in Combination After Pandemic Influenza A Antigen Stimulation with 95% Confidence Intervals by Study Day and Study Arm, Per Protocol Population
- Table 29: Percentage of CD8+ T Cell Subsets Expressing Markers Alone or in Combination After Pandemic Influenza A Antigen Stimulation with 95% Confidence Intervals by Study Day and Study Arm, Per Protocol Population

^{*}Wald test from Poisson regression used to compare groups.

^{95%} CIs calculated via 10,000 bootstrap samples.

Table 30: Summaries of Hemagglutination Inhibition Antibody Against A/Michigan/45/2015 X-275 (H1N1) by Study Day and Study Arm, Per Protocol Population

	Group A: 1 mg M-001 (N=X)	Group B: Placebo (N=X)
Day 1		
n	x	X
GMT (95% CI)	xxx.x(xxx.x,xxx.x)	xxx.x(xxx.x,xxx.x)
Titer ≥ 1:40 - %(95% CI)	x.x (x.x, x.x)	x.x (x.x, x.x)
Day 22		
n	x	X
GMT (95% CI)	xxx.x(xxx.x,xxx.x)	xxx.x(xxx.x,xxx.x)
Seroconversion - %(95% CI)	x.x (x.x, x.x)	x.x (x.x, x.x)
Titer ≥ 1:40 - %(95% CI)	x.x (x.x, x.x)	x.x(x.x, x.x)
Day 43		
n	x	X
GMT (95% CI)	xxx.x(xxx.x,xxx.x)	xxx.x(xxx.x,xxx.x)
Seroconversion - %(95% CI)	x.x (x.x, x.x)	x.x(x.x, x.x)

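### The primary T-cell comparison is a plain Poisson Wald test that ignores variation between subjects, so its p-values will usually be far too small

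*SAP*

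**What the plan says.** Protocol section 11.1 states the primary hypothesis as a ratio of GMPs equal to 1, and section 11.5.4 plans a t-test between arms at 14 days after dose 2. SAP section 12 changes this: "Instead of utilizing a normal approximation, a Poisson regression model will be fit to test for differences between study arms". The only reason given is that the data format had been confirmed.

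SAP section 8.1 defines the new model: "the following Poisson regression model will be fit for each combination of proteins of interest". Y is the number of cells showing a given marker pattern; "X is an indicator variable for Group A, and Z (the offset) is the total number of T cells in each sample". The Table 22 mock-up repeats the method in its footnote: "Wald test from Poisson regression used to compare groups". The GMPs printed beside each p-value carry per-arm bootstrap intervals.

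SAP section 5 keeps the power calculation for a two-sided t-test: "assuming the standard deviation of log GMP is 0.75, the study will have 80% power to detect a 2.5-fold increase". It then adds: "Utilizing different tests instead of those based on Normal approximations could increase the power from what is shown". It also says how the p-values will be read: "p-value thresholds of p<0.001, p<0.01, and p<0.05 will be considered as strong, moderate, and weak evidence of differences between study arms".

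**The concern.** Counts may be a reason to leave the t-test, but they are not a reason to drop between-subject variance. A Poisson model with only an arm term assumes every sample in an arm has the same underlying rate, so all scatter is counting noise. The SAP's own planning SDs say otherwise.

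The test also answers a different question. The Poisson coefficient compares pooled arithmetic rates, while the hypothesis, the power table and the displayed GMPs are all geometric.

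Table 22 has 37 rows (32 exclusive patterns and 5 any-marker rows), so CD4 and CD8 together give 74 tests. These p-values are the only formal between-arm evidence on the primary immunogenicity objective. They enter the topline report, which protocol section 11.5 allows to be used for planning further trials and for publication. If the variance is understated, labels of weak, moderate or strong evidence will often appear with no vaccine effect.

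**Working it through.** **1. The plan's own figure.** Two-sided t-test, alpha 0.05, SD on log10. SAP Table 5 reproduces within 2 points in every cell: for example, 2-fold at SD 0.50 gives 90.5/87.3 (SAP 90/87 for N=60/54), and 3-fold at SD 0.75 gives 93.3/90.6 (SAP 93/90). For 2.5-fold at SD 0.75, power is 82.2% at 60 per arm and 80.2% at 57 (60 less the SAP's 5% exclusions). The stated 80% holds for the t-test. It was not redone for the Poisson test.

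**2. Variance used by the Poisson Wald test.** With one arm indicator and an offset, the estimate is ln[(SA/ZA)/(SB/ZB)], where SA and SB are total positive cells per arm and ZA and ZB total cells. Its model variance is exactly 1/SA + 1/SB. A fitted model confirmed this: SE 0.047975 from the software and from the formula. Between-subject spread does not enter.

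**3. Variance the data would have.** If subject rates are log-normal with log10 SD s and the mean positive count per sample is mu, the true variance is larger by the factor

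1 + mu × (exp((s × ln 10)²) − 1).

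Example: s = 0.50, median 10 cells.
- (0.50 × 2.3026)² = 1.325, and exp(1.325) − 1 = 2.764.
- mu = 10 × exp(1.325/2) = 19.4.
- Factor = 1 + 19.4 × 2.764 = 54.6, so the true SE is √54.6 = 7.4 times the SE used.
- Approximate size = 2Φ(−1.96/7.4) = 79%. Simulation gives 77%.

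By this formula, size reaches 10% at mu = 1.07 (SD 0.25) or 0.15 (SD 0.50), and 50% at mu = 18.9 or 2.7. It overstates for sparse subsets at SD 0.75, so simulation is used there.

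**4. Simulated size with no vaccine effect.** 57 per arm, log-normal subject rates, Poisson counts, equal cell totals, 20,000 trials per scenario. Cells per sample are assumed, because the documents do not give them.

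| Median positive cells per sample | p<0.05, SD 0.25/0.50/0.75 | p<0.001, SD 0.25/0.50/0.75 |
|---|---|---|
| 0.1 | 4% / 10% / 36% | – |
| 1 | 10% / 40% / 73% | 0.6% / 16% / 57% |
| 3 | 20% / 61% / 84% | – |
| 10 | 41% / 77% / 92% | 16% / 63% / 85% |
| 100 | 78% / 93% / 98% | 63% / 88% / 96% |

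A separate simulation at 60 per arm agrees within about 2 points.

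**5. Sensitivity to assumptions.**
- *Planning SD already includes counting noise.* Size is 30%/75%/92% at 10 cells and 77%/92%/97% at 100. At SD 0.25 and about 3 cells or fewer, counting noise alone accounts for the SD (0.434/√3 = 0.25), and size is close to nominal.
- *Gamma instead of log-normal rates* (same log10 SDs, cell totals varying with CV 50%). Size is 9%/18%/25% at a mean of about 1 cell, 38%/58%/67% at about 11 and 76%/86%/89% at about 110.
- *All-negative rows (one CD4, one CD8).* The planning SDs cannot apply there. With about 100,000 cells per sample and SD 0.25 or 0.50 for the positive fraction, size was near 0% when positives were 0.01% of cells and 46% to 85% when they were 1%.

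**6. Alternatives in the log-normal scenarios.** A t-test on log10 values with 0.5 added to the count gives 4.7% to 5.3%. Quasi-Poisson gives 3.0% to 5.6%. A sandwich variance alone still gives 10% to 12% at SD 0.75.

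**The case against.** **The SAP writes only the mean model, so the standard error is unstated.** This is true as far as it goes. But the model is named as Poisson regression with a Wald test in two places, and the default calculation is the one above. Leaving the variance unstated does not protect the analysis.

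**The size of the error rests on inputs nobody has seen.** There are no cell counts, the SDs are a planning grid, and SD 0.75 is stated for IFN-γ subsets only. The log-normal is heavy-tailed at SD 0.75, and gamma rates give much smaller inflation at about 1 cell. This stands: the percentages are conditional, and the low-SD, low-count entries disappear if the planning SD includes counting noise. It does not rescue subsets with around 10 or more positive cells per sample, where every variant tried gives at least 30%.

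**The analyses are labelled non-confirmatory, the change is disclosed, and GMPs with bootstrap intervals sit beside each p-value.** The label is used in SAP sections 5 and 6.8 to justify no multiplicity adjustment; it does not excuse a single test whose nominal 5% may be 40% or more. The bootstrap intervals are per arm and give no between-arm ratio or test. The mITT sensitivity analysis changes the population, not the stated test.

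**The smallest repair is to estimate dispersion, not to bring back the t-test.** This is a fair point. Quasi-Poisson controls size, and the log-normal generator favours the log t-test on power. The t-test is preferred because it matches the protocol's hypothesis, the GMPs displayed and the power calculation.

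**Conclusion.** The concern holds. As written, the primary Day 36 test treats cells as the unit of replication and contradicts the SAP's own variance assumption. At the planning SDs its false-positive rate is well above 5%, except for very sparse subsets with low SD. It ranges from about 10% at 1 cell and SD 0.25 to over 90% at 100 cells and SD 0.50 or more.

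The missing variance term is certain from the text and the algebra. The exact percentages depend on the assumed cell counts, the distribution of subject rates and whether the planning SD includes counting noise. The plan should be corrected before the primary p-values are used.

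**What to change.** Make the primary Day 36 test one that includes between-subject variance and matches the GMP hypothesis. Suggested SAP text:

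> Day 36 percentages, computed with 0.5 added to the positive-cell count, will be log10-transformed and compared between arms by a two-sided t-test. The ratio of GMPs and its 95% CI will be reported.

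In addition:
- State the zero rule for the displayed GMPs. SAP section 3.3 says they "are calculated as the product of the observed percentages raised to the 1/Nth root", so one zero makes the whole GMP zero. At a median of 1 cell, 37% to 41% of samples would be zero.
- Use a count model only with estimated dispersion (quasi-Poisson or negative binomial), either as a sensitivity analysis or for very sparse subsets above a share of zeros fixed in advance. Do not rely on a sandwich variance alone.
- Delete or qualify the section 5 sentence suggesting that other tests could raise power.
- Clarify the denominator. Section 8.1 refers to all T cells counted, while section 4.5.2 reads as percentages of CD4 and of CD8 cells.

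**Cost.** SAP wording and a few lines of code; no new data. P-values will be less favourable. Adding 0.5 shrinks ratios in sparse subsets. For a true 2.5-fold effect at SD 0.75:

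| Median cells | Estimated ratio | Log t-test power | Quasi-Poisson power |
|---|---|---|---|
| 100 | 2.49 | 80% | 42% |
| 10 | 2.40 | 78% | 42% |
| 1 | 1.89 | 69% | 41% |
| 0.1 | 1.29 | 43% | 33% |

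At SD 0.25 the two tests have nearly equal power.

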5.4. Treatment Assignment Procedures

5.4.1. Randomization Procedures

Per International Conference on Harmonisation (ICH) guideline E6: Good Clinical Practice (GCP), screening records will be kept at each participating VTEU site to document the reason why an individual was screened, but failed trial entry criteria. The reasons why individuals failed screening will be recorded in the Statistical and Data Coordinating Center's (SDCC) AdvantageEDCSM (Electronic Data Capture System).

Once consented and upon entry of demographic data and confirmation of eligibility for this trial, the subject will be enrolled. One hundred twenty subjects will be randomly assigned to one of 2 treatment arms, as shown in [Table 1](#). Randomization will be stratified based upon prior receipt of the 2017-2018 influenza vaccine. The list of randomized treatment assignments will be prepared by statisticians at the SDCC and included in the enrollment module for this trial. AdvantageEDC will assign each volunteer a treatment code from the list after demographic and eligibility data have been entered into the system. A designated individual at each site will be provided with a treatment key, which links the treatment code to the actual treatment assignment, which will be kept in a secure place.

Instructions for use of the enrollment module are included in the AdvantageEDC User's Guide. Manual back-up randomization procedures are provided in the MOP for use in the event that the site temporarily loses access to the Internet or the online enrollment system is unavailable.

The randomization scheme for this study is presented in [Table 1](#) Table 1.

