- Approximately 60 mL of venous blood will be collected prior to the first study vaccination for isolation of PBMCs.
- Subjects will be enrolled in AdvantageEDC and randomly assigned to a treatment arm prior to the first study vaccination.
- Pre-administration reactogenicity assessments will be performed prior to the first study vaccination to establish baseline. Subjects will then receive a single dose of study vaccine via IM injection in the deltoid muscle of the preferred arm. The site of injection (right or left arm) and time of administration will be recorded on the appropriate data collection form. Subjects will be observed in the clinic for at least 20 minutes after the first study vaccination. The study vaccination site will be examined, and any AE/SAEs will be assessed and recorded on the appropriate data collection form prior to discharge from the clinic.
- Subjects will be provided with a Memory Aid and other study-related materials to record daily oral temperature, solicited injection site and systemic reactions, any unsolicited AEs, and concomitant medications/vaccinations. Subjects will be encouraged to take their temperature around the same time each day for 8 days post vaccination. Subjects will be instructed on how to use the Memory Aid and how to measure and record AEs prior to discharge from the clinic. Subjects will be instructed to notify the study center if they develop any severe reactions after the first study vaccination. If the site PI or appropriate sub-I deems the reaction severe enough, s/he will give further instructions on the proper course of action, including a return to the clinic for immediate evaluation if appropriate.

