3.2. Outcome Measures

3.2.1. 3.2.1 Primary Outcome Measures

Safety

- Occurrence of vaccine-related SAEs from the time of the first study vaccination (M-001 or placebo) through approximately 6 months after the second M-001 study vaccination
- Occurrence of solicited injection site and systemic reactogenicity events on the day of each study vaccination through approximately 7 days after each M-001 vaccination
- Occurrence of clinical safety laboratory adverse events from the time of each study vaccination of M-001 through approximately 7 days after each M-001 vaccination

Immunogenicity

• Geometric Mean Percentage of T cell subsets expressing perforin, CD107a, IFN-γ, TNF-α, and IL2, alone or in combination, in CD4 and CD8 cells after stimulation with M-001 component peptides at baseline (Day 1) and 14 days after the second dose of M-001

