4.4.3. Method of Assigning Subjects to Study Arms (Randomization)

Enrollment/randomization is done through the enrollment module in the electronic data capture system, maintained by the SDCC.

Eligible subjects are randomized and assigned in a [1:1] ratio to receive two priming doses 21 days apart of either M-001 (Group A) or saline placebo (Group B), followed by seasonal IIV4 vaccination (all groups). Randomization is stratified by prior receipt of the 2017-2018 influenza vaccine and by site. The randomization is based on a variable blocked scheme to provide an approximately balanced allocation to the study arms during the study.

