6.7. Multicenter Studies

Data will be pooled across all three clinical sites. Center effects are not anticipated because the sites are using standardized procedures for vaccination and assessment of solicited and unsolicited adverse events, and the study relies on central laboratories for the assessment of immunogenicity endpoints.

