14.2 Efficacy/Immunogenicity Data

Table 22: Geometric Mean Percentage (GMP) of CD4+ T Cell Subsets Expressing Markers Alone or in Combination After M-001 Stimulation with 95% Confidence Intervals by Study Day and Study Arm, Per Protocol Population*

Study	Dowf	CD107:	IFN-	TNF-	11.2	Gro	up A: 1 m	g M-001	(Group B:	Placebo	n realizar
Day	Perforin	CD107a	γ	α	IL2	n	GMP	95% CI	n	GMP	95% CI	p-value ^x
				•		Pri	imary End	lpoint				
Day 36	+	+	+	+	+	х	X.X	x.x, x.x	Х	X.X	X.X, X.X	
	+	+	+	+	-	х	X.X	x.x, x.x	Х	X.X	X.X, X.X	
	+	+	+	-	+	х	X.X	x.x, x.x	Х	X.X	X.X, X.X	
	+	+	+	-	-	х	X.X	x.x, x.x	Х	X.X	X.X, X.X	
	+	+	-	+	+	х	X.X	x.x, x.x	Х	X.X	X.X, X.X	
	+	+	-	+	-	х	X.X	x.x, x.x	Х	X.X	X.X, X.X	
	+	+	-	-	+	х	X.X	x.x, x.x	Х	X.X	X.X, X.X	
	+	+	-	-	-	х	X.X	x.x, x.x	Х	X.X	X.X, X.X	
	+	-	+	+	+	х	X.X	x.x, x.x	Х	X.X	X.X, X.X	
	+	-	+	+	-	х	X.X	x.x, x.x	Х	X.X	X.X, X.X	
	+	-	+	-	+	х	X.X	x.x, x.x	Х	X.X	X.X, X.X	
	+	-	+	-	-	х	X.X	x.x, x.x	Х	X.X	X.X, X.X	
	+	-	-	+	+	х	X.X	x.x, x.x	Х	X.X	X.X, X.X	
	+	-	-	+	-	х	x.x	x.x, x.x	Х	X.X	X.X, X.X	
	+	-	-	-	+	х	X.X	x.x, x.x	Х	X.X	X.X, X.X	
	+	-	-	-	-	х	X.X	x.x, x.x	Х	X.X	X.X, X.X	
	-	+	+	+	+	х	X.X	x.x, x.x	Х	X.X	X.X, X.X	
	-	+	+	+	-	х	X.X	x.x, x.x	Х	X.X	X.X, X.X	
	-	+	+	-	+	х	X.X	x.x, x.x	Х	X.X	X.X, X.X	
	-	+	+	-	-	х	X.X	x.x, x.x	Х	X.X	X.X, X.X	
	-	+	-	+	+	х	X.X	x.x, x.x	Х	X.X	X.X, X.X	
	-	+	-	+	-	х	X.X	x.x, x.x	Х	X.X	X.X, X.X	
	-	+	-	-	+	х	X.X	x.x, x.x	Х	X.X	X.X, X.X	
	-	+	-	-	-	х	X.X	x.x, x.x	Х	X.X	X.X, X.X	
	-	-	+	+	+	х	X.X	x.x, x.x	Х	X.X	X.X, X.X	
	-	-	+	+	-	х	X.X	x.x, x.x	X	X.X	X.X, X.X	
	-	-	+	-	+	х	X.X	x.x, x.x	Х	X.X	X.X, X.X	
	-	-	+	-	-	X	X.X	x.x, x.x	Х	X.X	X.X, X.X	
	-	-	-	+	+	х	X.X	x.x, x.x	Х	X.X	X.X, X.X	
	-	-	-	+	-	х	X.X	x.x, x.x	Х	X.X	X.X, X.X	
	-	-	-	-	+	Х	X.X	x.x, x.x	х	X.X	X.X, X.X	

Study	D. C.	CD107	IFN-	TNF-	11.2	Gro	up A: 1 m	g M-001	(Group B:	Placebo	
Day	Perforin	CD107a	γ	α	IL2	n	GMP	95% CI	n	GMP	95% CI	p-value ^x
	-	-	-	-	-	X	X.X	X.X, X.X	X	X.X	X.X, X.X	
	+	+/-	+/-	+/-	+/-	X	X.X	X.X, X.X	X	X.X	X.X, X.X	
	+/-	+	+/-	+/-	+/-	X	X.X	x.x, x.x	х	X.X	X.X, X.X	
	+/-	+/-	+	+/-	+/-	X	X.X	x.x, x.x	х	X.X	X.X, X.X	
	+/-	+/-	+/-	+	+/-	X	X.X	X.X, X.X	X	X.X	X.X, X.X	
	+/-	+/-	+/-	+/-	+	X	X.X	X.X, X.X	X	X.X	X.X, X.X	

Exploratory Endpoints

Repeat for Baseline, Day 15, Day 43, Day 78, Day 172, Day 186, and Day 200 without p-value column.

Notes: N = number of subjects in Per Protocol population.

Tables with similar format:

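### The primary Day 36 comparison uses arm alone and leaves out the Day 1 percentage and the randomisation strata

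*SAP*

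**What the plan says.** SAP 8.1 models the count of positive cells in each sample, with the total T cell count as offset. Apart from the intercept it has a single term, where "X is an indicator variable for Group A", and the arm coefficient gets a Wald test. SAP 12 records this as a change from the protocol: "a Poisson regression model will be fit to test for differences between study arms". The protocol's own test (11.5.4) was an unadjusted t-test.

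The primary outcome measure (protocol 3.2.1, SAP 3.2.1) gives the percentages at two times: "at baseline (Day 1) and 14 days after the second dose of M-001". Protocol 7.1 schedules the Day 1 sample: "Approximately 60 mL of venous blood will be collected prior to the first study vaccination for isolation of PBMCs". SAP 3.3 defines Day 1 as the cellular baseline. In the Table 22 mock-up, however, only Day 36 is tested. The instruction for the other days is "Repeat for Baseline, Day 15, Day 43, Day 78, Day 172, Day 186, and Day 200 without p-value column", under a label that calls them exploratory.

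On strata, protocol 5.4.1 says "Randomization will be stratified based upon prior receipt of the 2017-2018 influenza vaccine", while SAP 4.4.3 says "Randomization is stratified by prior receipt of the 2017-2018 influenza vaccine and by site". SAP 6.4 covers covariates and subgroups by title but names no covariate. SAP 6.7 pools the sites and gives a reason: "Center effects are not anticipated because the sites are using standardized procedures for vaccination", together with the use of central laboratories. No section gives a reason for leaving out Day 1 or prior vaccination, and no sensitivity analysis adds them. The mITT analysis changes the population only.

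**The concern.** A subject's T cell response before vaccination may well predict the response at Day 36, and here it is measured in advance with the same assay. Leaving it out has two consequences. The interval for the GMP ratio is wider than it need be. Any chance difference between the arms on Day 1 also passes into the Day 36 ratio in proportion to the correlation. The strata were important enough to control at randomisation, yet they are dropped from the analysis.

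Bias is not at stake. SAP 5 and 6.8 also declare these analyses not confirmatory. Even so, SAP 5 grades the evidence by p-value thresholds of 0.05, 0.01 and 0.001, so the precision of each comparison affects what is reported.

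**Working it through.** **Inputs from the documents** (protocol 11.3.4; SAP 5): 60 per arm; SD 0.75 on the log10 scale; 2.5-fold ratio, so difference log10(2.5) = 0.398; two-sided alpha 0.05; up to 5% excluded (57 per arm); 10% dropout in the power table (54 per arm). **Assumed, because the documents do not give it:** the Day 1 to Day 36 correlation r, taken from 0.1 to 0.7.

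**The plan's figure.** SE = 0.75 × √(2/60) = 0.137. Noncentrality = 0.398/0.137 = 2.91 on 118 df, which gives power 82.2%. At 57 per arm power is 80.2%, and at 54 it is 78.0%. The stated 80% therefore holds as a minimum at 60 and almost exactly after 5% loss.

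**With adjustment.** Residual SD = 0.75 × √(1 − r²). Day 1 (1), prior vaccination (1) and three sites (2) use 4 df, leaving 2n − 6. The strata are given no explanatory value in this table.

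| r | Residual SD | Power, 60/arm | Power, 57/arm | Power, 54/arm | Fold detectable at 80%, 60/arm |
|---|---|---|---|---|---|
| unadjusted | 0.750 | 82.2% | 80.2% | 78.0% | 2.44 |
| 0.1 | 0.746 | 82.5% | 80.6% | 78.4% | 2.43 |
| 0.2 | 0.735 | 83.7% | 81.7% | 79.6% | 2.39 |
| 0.3 | 0.715 | 85.6% | 83.7% | 81.7% | 2.34 |
| 0.5 | 0.650 | 91.4% | 90.0% | 88.4% | 2.16 |
| 0.7 | 0.536 | 98.1% | 97.6% | 96.9% | 1.89 |

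The unadjusted size with equal precision is 60/(1 − r²): 66 per arm at r = 0.3, 80 at 0.5 and 118 at 0.7. At r = 0 the adjusted power is still 82.2%.

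**Strata alone.** If they explain an assumed 1%, 5% or 10% of the variance, power at 60 per arm is 82.5%, 84.1% or 85.9%.

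**Chance imbalance.** If the Day 1 SD is also 0.75, the arm difference at Day 1 has SE 0.137 log10, or 1.37-fold. A one-SE imbalance moves the unadjusted Day 36 ratio by 10^(0.137r): a factor of 1.03, 1.10, 1.17 or 1.25 at r = 0.1, 0.3, 0.5 or 0.7.

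**Does a covariate help the planned test?** This was simulated with 1,500 trials per setting, 60 per arm, log-normal percentages with SD 0.75 log10 and Poisson counts. Three cell-count settings were assumed: median 0.05% of 100,000 cells, 0.05% of 20,000, and 0.01% of 50,000, giving about 1%, 8% and 15% zeros. Strata were not simulated, and r was 0.3, 0.5 and 0.7. Type I error at nominal 5%:

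- Poisson Wald as planned: 86.6% to 96.8%
- Poisson Wald plus Day 1: 84.9% to 96.2%
- Quasi-Poisson plus Day 1: 7.6% to 21.2%
- Sandwich variance (HC3) plus Day 1: 6.7% to 10.2%
- ANCOVA on log10 percentages, half a cell added to each count: 4.3% to 5.7%

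ANCOVA power for 2.5-fold at r = 0.3, 0.5 and 0.7 was 83.3%, 90.7% and 97.5% with 1% zeros, and 79.5%, 86.9% and 93.9% with 15% zeros. The unadjusted t-test gave 81–84% and 77–79%.

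**The case against.** The strongest reply is that nothing required is missing. The protocol's test was unadjusted, the sample size was computed for it, and 80% power is met without covariates. The comparison is unbiased and declared not confirmatory. Day 1 is tabulated by arm and box-plotted, protocol 11.5.4 places the tested endpoint at 14 days after dose 2, and naming two time points does not promise adjustment. All of this is correct. It limits the point to efficiency and to protection against imbalance.

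The benefit also depends on an unknown r. Counting noise lowers the observed correlation in sparse subsets, and Table 22 has 37 marker rows for each cell type. In a simulation with about 54% zeros, a true r of 0.3 fell to about 0.19, and power was 65.7% unadjusted against 67.4% adjusted. With about 70% zeros it was 53.5% against 54.6%. At a true r of 0.5 the gains were about 5 and 4 points, against 9 in closed form. This stands: one range of r does not describe every row, and the sparsest rows gain little.

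Two further objections stand. The strata add little, and SAP 6.7 gives a reason for pooling sites. The larger defect is the Poisson variance, which a covariate does not cure. The second objection governs the remedy: adjustment is worth having only with a valid variance. None of this supplies a reason for omitting a baseline that is already collected and costs 1 df.

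**Conclusion.** The concern holds, as a change that should be made rather than one on which validity depends. The test uses arm alone, Day 1 belongs to the stated primary outcome measure, and its omission and that of prior vaccination are unexplained.

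At 60 per arm the gain over 82.2% is 0.3 to 1.5 points for r of 0.1 to 0.2, 3.4 points at 0.3, 9.2 at 0.5 and 15.9 at 0.7, and smaller in sparse subsets. These figures assume log-normal percentages with SD 0.75 and a valid log-scale test; they do not apply to the Poisson Wald test. Both r and the cell counts are assumptions. The disagreement over strata between protocol 5.4.1 and SAP 4.4.3 is plain from the text and needs no assumption.

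**What to change.** Replace the SAP 8.1 test with ANCOVA of the Day 36 log10 percentage on arm, Day 1 log10 percentage and the strata as randomised. Report the adjusted GMP ratio with its 95% CI. This returns to the log scale of the hypothesis in protocol 11.1. Four details need writing down:

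- **Strata.** Reconcile protocol 5.4.1 with SAP 4.4.3. Include 2017-18 vaccination, and include site if it was a stratum.
- **Zeros.** State one rule for Day 1, Day 36 and the GMPs in SAP 3.3, for example adding half a cell to every count before dividing by total T cells. The note to Listing 18 shows that zeros are expected, and a geometric mean is zero if any value is zero.
- **Missing Day 1.** The mITT definition (SAP 6.3.1) does not require a Day 1 result. State a rule, for example the Day 1 mean pooled over arms, as an exception to the no-imputation rule in SAP 6.5.
- **SAP 12.** Record the change.

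If the count model is kept, give it the same covariates and a subject-level robust or overdispersed variance. Take its p-value from re-randomisation within strata, because neither variance held 5% in the simulation.

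The cost is SAP wording and code, with no new data, and 4 of 118 residual degrees of freedom. The rules for zeros and missing Day 1 values must be fixed before unblinding.
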